22.8 Appendix 8 – Data Collection Form

Data Collection Form	
Participant Number:	
Data Collection at Time of Surgery	
Age:	
Ethnicity:	
Clinical diagnosis (pre-op):	
Site:	
Length of wound (mm):	
Width of wound (mm):	
Number and type of interrupted subcuticular sutures:	
Number and type of interrupted percutaneous sutures:	
Drug history (immunosuppressants or anticoagulants):	
Diabetic diagnosis:	
Smoking history:	
History of keloid scar or hypertrophic scarring:	
Normal length of time recommended for suture removal in this case:	

Timing of Suture Removal to Reduce Scarring in Skin Surgery

Data Collection at 3 Month Follow-up			
Stitch marks visible (yes/no):			
POSAS:	Patient scale	Pain:	
		Itch:	
		Colour:	
		Stiffness:	
		Thickness:	
		Irregular:	
		Overall Opinion (not part of total score):	
	Total:		
	Observer Scale	Vascularity (pale; pink; red; purple; mix):	
		Pigmentation (hypo; hyper; mix):	
Thickness (thicker; thinner):			
Relief (more; less; mix):			
Pliability (Supple; stiff; mix):			
Surface area (expansion; contraction; mix):			
Overall Opinion (not part of total score):			
Total:			
VAS:			
Wound infection (defined using CDC criteria for surgical site infection)*:			
Wound dehiscence:			
Significant post-operative bleeding:			
Any other comments:			
* Infection occurs within 30 days after the operation and infection involves only skin and subcutaneous tissue of the incision and at least one of the following: 1.Purulent drainage with or without laboratory confirmation, from the superficial incision 2.Organisms isolated from an aseptically obtained culture of fluid or tissue from the superficial incision			

Timing of Suture Removal to Reduce Scarring in Skin Surgery

- 3. At least one of the following signs or symptoms of infection: pain or tenderness, localized swelling, redness, or heat and superficial incision is deliberately opened by surgeon, unless incision is culture-negative
- 4. Diagnosis of superficial incisional SSI made by a surgeon or attending physician

Timing of Suture Removal to Reduce Scarring in Skin Surgery

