13. RESEARCH QUESTION

In patients undergoing wide local excision and primary wound closure for treatment of skin cancer does earlier removal of percutaneous sutures (7 days rather than 10 days) reduce the incidence of suture marks assessed at 3 months post-operatively.

Secondary questions:

Does earlier suture removal have an impact (negative or positive) on overall scar cosmesis and wound complication rates* (as assessed by the clinician and the patient)?

Timing of Suture Removal to Reduce Scarring in Skin Surgery

**Risk of post-operative bleeding, risk of surgical site infection, risk of wound dehiscence (opening up of scar)*

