14. AIMS AND OBJECTIVES

Aim:

To test the feasibility of conducting a definitive trial looking at outcomes for earlier removal of percutaneous sutures (7 days versus 10 days) for patients undergoing wide local excision and primary closure for treatment of skin cancers on the chest or back in dermatology.

Objectives:

1. To work out the standard deviation of the outcome measure (suture marks versus no suture marks) in order to estimate a sample size required for a properly powered RCT. (The incidence of 'suture marks' and the impact that these have on patients is currently unknown).
2. To provide some preliminary data on the incidence of wound complications and overall scar cosmesis in each group and ensure that this does not differ from expected:
 - a. *Overall cosmesis*
 - b. *Risk of post-operative bleeding*
 - c. *Risk of surgical site infection*
 - d. *Risk of wound dehiscence (opening up of scar)*
3. To assess the willingness of participants to be randomized.
4. To assess the willingness of clinicians to recruit patients.
5. To assess follow-up rates and adherence.
6. To assess the characteristics and ease of use of the proposed outcome measures including POSAS for scar assessment, a VAS, and patient reported outcome for complications including dehiscence and infection.
7. To gain feedback from patients at their three month follow up appointment on the patient pathway including the trial information leaflet and consent process.
8. To collect data on any additional costs that we may incur that have not been planned for, to inform costing for a future trial e.g. additional printing of PIS or consent forms or additional clinic booking slots
9. To use the gathered data to refine the design of the proposed RCT.

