16.4 Randomization and Blinding

Timing of Suture Removal to Reduce Scarring in Skin Surgery

Patients will be randomized into two groups following acceptance into the trial. A dermatology nurse, independent to the research trial and not involved in data collection or analysis, will use a random number generator to prepare 60 sealed envelopes, labelled 'participant 1' to 'participant 60'. These sealed envelopes will contain a slip of paper that either says 'suture removal at 7 days group' or 'suture removal at 10 days group'. During preparation of these envelopes using the random number generator, an odd number produced will be 'suture removal at 7 days group' and an even number will be 'suture removal at 10 days group'. The nurse who prepares these envelopes will be independent of the research trial to avoid any selection bias and maintain concealment. They will also have completed a 'Good Clinical Practice' (GCP) certificate. The surgeon and members of the research team involved in data gathering and analysis will be blinded to allocation.

After written consent to the trial has been gained, and excision of the lesion performed, the patient will leave the theatre room alongside one of our dermatology nurses/HCAs who is independent of the research team in order to maintain concealment and prevent selection bias. The patient and nurse/HCA will open one of the sealed envelopes, in numbered order, to reveal which arm of the trial they have been allocated to. The patient will be requested not to disclose which arm of the trial they were in. The theatre nurse or healthcare assistant will then discuss the post-operative wound care and timing of suture removal with the patient.

Patient blinding is not feasible as patients need to know which day to have their sutures removed post-surgery.

Before the patient leaves the department, an appointment will be booked with their GP for suture removal at either 7 or 10 days. If their GP does not have the capacity to remove the sutures on the given day, an appointment will be booked within the dermatology department on the given day for suture removal.

If the patient cannot attend the appointment for suture removal specifically on day 7 or 10, they will be removed from the study.

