22.13 Appendix 13 – Standard Operating Procedure (SOP) for Suture Removal

Standard Operating Procedure (SOP) for Suture Removal

Aim:

The nurse or healthcare assistant is able to assess the wound post operatively, remove the superficial sutures appropriately and recommend simple post-operative wound care

[figure not shown]
Procedure:

1. Confirm the patients identity and gain consent for removal of sutures
2. Wash hands and prepare procedure trolley surface aseptically with correct equipment:
 - a. Disposable Fine tipped non toothed forceps
 - b. Dressing pack – containing sterile gloves and gauze
 - c. Disposable sharp surgical scissors
 - d. Sterile normal saline if required
3. Wash hands and use non-sterile gloves to remove current dressing (if any)
4. The wound should specifically be checked for signs of dehiscence, infection or poor wound healing. If this is the case, medical advice should be sought
5. If the wound shows signs that it may dehisce if sutures are removed at the time, then consider keeping sutures in for removal at a later date at the discretion of the healthcare professional. These patients will be excluded from the study. If this is the case, it is important that you let the study team know by contacting us on the below details.
6. Removal of simple percutaneous interrupted sutures:
 - a. Wash hands and don sterile gloves
 - b. Gently grasp the knot of a suture with forceps and raise it slightly
 - c. Place the tip of the suture scissors directly under the knot or on the side close to the skin
 - d. Gently cut the suture and pull it out gently across the wound with the forceps
 - i. Remove the suture across the wound to minimise any exposed suture passing through the skin and wound during the removal, this can lead to infection. Cutting the correct part of the suture (part directly under the knot on the side closest to the skin), will bypass this from happening
 - e. Place steri-strips on the sites that sutures have been removed. These are applied in opposite directions with a small amount of tension to take tension away from the wound. Educate patient to let the steri-strips fall off naturally (usually 1-2 days). No further treatment to the wound should be required.

Timing of Suture Removal to Reduce Scarring in Skin Surgery

- f. Continue to remove sutures until all sutures have been removed
- g. The application of a suitable wound dressing can be applied at the healthcare professionals discretion

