- h. Discard sutures as per local policy and record the intervention in the medical notes
- i. Dispose any sharps and used instruments safely according to trust policy

If there have been any early post-operative complications, such as dehiscence, infection or poor wound healing, please could you contact the study organisers on the details below.

[name] (CI), [name] (PI), [name] (PI)
Dermatology Department
Heavitree Hospital
Royal Devon and Exeter NHS Foundation Trust
[name]
[name]
[contact]

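### Adherence to the randomised removal day is an objective, but the available documents plan no way for the trial to learn the actual day of an uneventful suture removal

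*Combined protocol and SAP*

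**What the plan says.** The research question (section 13) is whether "earlier removal of percutaneous sutures (7 days rather than 10 days) reduce the incidence of suture marks assessed at 3 months post-operatively". Objective 5 in section 14 reads "To assess follow-up rates and adherence".

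Under section 16.4, before the patient leaves the department, "an appointment will be booked with their GP for suture removal at either 7 or 10 days". The dermatology department is the fallback if the practice has no capacity that day. The same section adds: "If the patient cannot attend the appointment for suture removal specifically on day 7 or 10, they will be removed from the study".

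The Data Collection Form (Appendix 8) has a block completed at surgery and a block completed at 3 months. Its one timing item, in the surgery block, is "Normal length of time recommended for suture removal in this case".

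The SOP for suture removal (Appendix 13) covers three situations:
- Sutures kept in because the wound may dehisce: "If this is the case, it is important that you let the study team know by contacting us on the below details".
- Complications: "If there have been any early post-operative complications, such as dehiscence, infection or poor wound healing, please could you contact the study organisers".
- Any removal: "Discard sutures as per local policy and record the intervention in the medical notes".

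The GP letter (Appendix 12) names both removal days as the subject of the study and requests no information in return.

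**The concern.** The day of removal is the only thing that differs between the arms by design. One purpose of a feasibility study is to find out whether removal on an exact day, largely outside the department's control, can be delivered. That needs the actual day for each participant, and the plan does not collect it.

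Two parts of the plan depend on this item. Objective 5 cannot be met for the randomised timing without it. The exact-day rule in 16.4 can be applied when a clash is known at booking, but no source of information is named for a visit that moves later. The requirement in 19.6 to document and report deviations has the same gap, since a deviation must first be seen.

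**Working it through.** **1. Is the removal day captured anywhere?** Each place where it could be was checked:

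- Section 16.2, data before and just after surgery: patient history, wound size, number and type of sutures. No removal day.
- Section 16.6, data at 3 months: POSAS, VAS, complications, photographs. No removal day.
- Appendix 8: no block for the removal visit, no date of surgery, no date of removal, no place of removal, no days in situ.
- Appendix 13: contact is requested on two triggers, sutures kept in or a complication. Otherwise the record stays in the remover's medical notes.
- Appendix 12: nothing is to be sent back.

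A removal without a wound problem, on a day other than the one booked, meets neither trigger and has no field on the form.

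**2. What this does to the plan's problem-detection argument.** Section 18.4 takes p = 0.05 and about 95% confidence of seeing a problem at least once.

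- Plan's figure: n = ln(1 − 0.95) / ln(1 − 0.05) = 58.4, rounded up to 59. The short form is 3/p = 3/0.05 = 60. Both reproduce.
- Suppose off-schedule removal is a problem with p = 0.05, and the trial can see the day for a share s of 60 removals. The chance of at least one sighting is 1 − (1 − 0.05s)^60. The documents do not give s, so a range is shown:

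| s (assumed) | Chance of seeing at least one |
|---|---|
| 1 | 95.4% |
| 0.75 | 89.9% |
| 0.5 | 78.1% |
| 0.25 | 53.0% |
| 0 | 0% |

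The 95% claim covers this problem only if the day is known for practically everyone.

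**3. What recording the day would give.** The approximate 95% half-width for adherence a is 1.96 × √(a(1 − a)/n). With n = 60 it is 10.1 percentage points at a = 80% and 5.5 at a = 95%. With n = 30 per arm it is 14.3 and 7.8 points.

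**4. What unseen shifts would do to the 3-day contrast.** The documents give no shift rate, so these are scenarios only:

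- Towards the other arm, 20% of each (day 10 to 8, day 7 to 9): 0.8×10 + 0.2×8 = 9.6 and 0.8×7 + 0.2×9 = 7.4, a contrast of 2.2 days.
- The same with 10%: 0.9×10 + 0.1×8 = 9.8 and 0.9×7 + 0.1×9 = 7.2, a contrast of 2.6 days.
- One day late in both arms, 20% of each: 0.8×10 + 0.2×11 = 10.2 and 0.8×7 + 0.2×8 = 7.2, a contrast of 3.0 days.
- Apart, 20% of each (day 10 to 11, day 7 to 6): 10.2 and 0.8×7 + 0.2×6 = 6.8, a contrast of 3.4 days.

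The contrast can shrink, stay the same or grow, and the planned dataset could not show which had happened.

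**The case against.** Much can be said for the plan. The booked date is fixed before the patient leaves. When removal takes place in the department, the date should be in the Trust's own notes. GP records could be requested, and the form's free-text comments field could hold a date. Delays because the wound may dehisce are reported under the SOP, and 19.6 requires deviations to be reported. Leaving the removal date off the 3-month form also protects the blinded assessor, because the day reveals the arm. The patient information sheet and consent form (Appendices 6 and 7) and the content of the flow chart (section 9) were not available, so an instruction there to report a moved visit cannot be excluded.

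All of this stands, and it rules out three stronger readings that a reader might infer:

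- *That the trial can never learn the day.* Retrieval is possible for at least some patients. What is missing is a planned route. The split between GP and departmental removals is not given either, so the share affected is unknown.
- *That the contrast is cut by about a quarter.* The fall from 3.0 to 2.2 days (27%) appears only if every moved visit moves towards the other arm. An equal delay in both arms leaves 3.0 days. Nothing in the documents converts days in situ into suture-mark rates.
- *That summarising a patient treated at day 8 within the 10-day arm is an error.* That is ordinary analysis as randomised, and section 19.1 calls the trial pragmatic. Rates under realistic adherence can be reasonable inputs for planning the definitive trial.

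What the objection does not supply is a data item for objective 5. A booked date is not a removal date, and records that might be retrieved are not planned data.

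**Conclusion.** The point holds as a gap in planned data capture. If the documents available are followed exactly, the actual removal day of an uneventful removal does not reach the trial. Adherence to the randomised timing then cannot be reported, and the exact-day rule in 16.4 cannot be applied to visits that move unannounced after booking. The size of any loss of contrast is unknown, and no single percentage should be attached to it. The descriptive analysis, the target of 60 and the as-randomised summaries are not put in doubt. The conclusion assumes that the patient pages and flow chart not available contain no reporting instruction. It matters because it concerns a stated objective and because a day not recorded at the time may be hard to recover later.

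**What to change.** Add a short return slip to the SOP, completed for every participant and not only when there is a problem. It should hold the participant number, date of surgery, date of removal, place of removal, whether all sutures were removed (yes/no), and the reason for any departure from the allocated day.

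Send it to a named unblinded person outside the assessment and analysis team. This should not be the nurse who prepares the envelopes, because 16.4 says that nurse takes no part in data collection. Edit 16.4 to name the role.

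Keep the slips apart from the 3-month form until all assessments are complete. Then report days in situ and adherence by arm under objective 5, with confidence intervals, and keep the main summaries by randomised arm.

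The cost is a one-page form, an SOP edit and a matching edit to 16.4. The downside is that practices must return a slip for every patient and some will need chasing. The return rate would itself be useful feasibility information.

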16.6 Data Collection at 3 Month Follow Up

Patients will be booked in for a 3 month follow-up appointment, as per their standard care pathway. Data collection at 3 month follow up will include completing a patient and observer scar assessment scale (POSAS) with regards to overall scar cosmesis, and also a visual analogue scale (VAS) in relation to suture marks specifically. We have chosen these tools as they are validated, well known scales to characterise scars subjectively and objectively [10].

The patient will be asked about any post-operative complications that were not detected at suture removal including wound infection, dehiscence, and significant post-operative bleeding (defined as bleeding requiring assessment by a healthcare professional). Assessment will be carried out by a member of the research team who will be blinded to trial allocation.

Photographs of the scar will be taken at the follow-up visit using the departmental camera to allow review of scar assessment at a later date if required. This will be directly uploaded onto their electronic patient record in line with Trust policy. Patients will be verbally consented for this at time of follow up, as per usual practice.

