17. DATA ANALYSIS METHODS

[name], Statistical advisor, Royal Devon and Exeter hospital has been consulted.

Data collection and input will be carried out by the research team who will be employed by the RDEFT and will comply with local and national information governance standards. A password-protected Excel spreadsheet will be set up on a Trust computer in the Dermatology Department - also password protected. All paper and electronic data will be collected and stored in compliance with data protection guidelines, good clinical practice in research guidance and Trust clinical governance policy.

A feasibility study will provide an opportunity to assess the data to be collected and the choice of appropriate statistical tests for a future definitive trial. Data analysis will involve statistical methods appropriate to the data collected. The statistical analysis for the feasibility study will be descriptive for each group as hypothesis testing is not an aim of the feasibility study and it is likely to be underpowered for that anyway. Descriptive statistics of baseline characteristics will be compared between study groups to demonstrate the effectiveness of randomisation. Continuous outcome

Timing of Suture Removal to Reduce Scarring in Skin Surgery

data will be tested for normality using the Shapiro Wilks test. If the data are found to be normally distributed, central tendency will be expressed using means and dispersion using standard deviation. If the data prove not to be Gaussian, and cannot easily be transformed, they will be summarized using medians, interquartile ranges and ranges. Mean (or median) differences and the standard deviation of the differences will be used to inform sample size calculations for a definitive trial. Confidence intervals will be derived wherever possible. Categorical data will be summarized as proportions and percentages as appropriate with associated confidence intervals. No attempt will be made at this stage to make formal comparisons of outcome measures – this will be done in the eventual definitive study. Summaries of secondary outcome measures will also be produced in a similar manner to the above.

All data management will adhere to GDPR compliance. Statisticians will be blinded to allocation arms.

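### The infection item on the data form is labelled surgical site infection but defined as superficial infection only, so a deeper wound infection falls outside the objective 2c rate

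*Combined protocol and SAP*

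**What the plan says.** Section 14 sets objective 2: "To provide some preliminary data on the incidence of wound complications and overall scar cosmesis in each group". Item c under it is "Risk of surgical site infection", and section 13 poses the same outcome as a secondary question. Neither place limits depth.

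The data form (section 22.8, Appendix 8) has one infection row, labelled "Wound infection (defined using CDC criteria for surgical site infection", with an asterisk to a footnote. The footnote sets two conditions that must both be met:

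- **Timing and depth:** "Infection occurs within 30 days after the operation and infection involves only skin and subcutaneous tissue of the incision".
- **Evidence:** one or more of four criteria. The first is "Purulent drainage with or without laboratory confirmation, from the superficial incision". The second is a positive culture from the same layer, the third is signs or symptoms with deliberate opening of that layer, and the fourth is "Diagnosis of superficial incisional SSI made by a surgeon or attending physician".

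Section 17 says how the item will be reported: "Categorical data will be summarized as proportions and percentages as appropriate with associated confidence intervals". It plans no formal comparison of outcomes.

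Infection is also reached elsewhere, without a depth limit. Section 16.6 says: "The patient will be asked about any post-operative complications that were not detected at suture removal including wound infection, dehiscence". Section 19.1 lists infection among the adverse events, whose incidence is to be recorded in both arms. The suture removal procedure (section 22.13, Appendix 13) asks staff to check for infection and to tell the study organisers of early complications. The form also has a free-text comments line.

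**The concern.** The name of the outcome and the rule that decides it do not match. The row and the objective name surgical site infection as a whole; the rule admits only the superficial part. A case is excluded because it extends deeper, so the rule leaves out the more extensive infections. An arm with one deeper infection could show a lower 2c rate than an arm with one superficial infection.

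Two things are at stake. First, objective 2 asks for complication incidence in each group and for a check that it is as expected; for infection, that check would rest on a subset of the named outcome. Second, objectives 6 and 9 use this study to assess the outcome measures and refine the definitive trial, so this is the time to find and repair a definition that does not fit its label.

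**Working it through.** **Step 1. Apply the rule to two cases.**

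| Requirement on the form | Superficial infection | Infection extending below subcutaneous tissue |
|---|---|---|
| Row label: surgical site infection | fits | fits |
| Footnote: confined to skin and subcutaneous tissue | met | not met |
| Footnote: one or more of criteria 1 to 4 | can be met | each criterion is worded for the superficial incision |
| Counts in the 2c rate | yes | no |

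The two conditions are joined by *and*, so failing the depth condition is enough to exclude the case. A physician's diagnosis does not bring it back, because criterion 4 accepts only a superficial diagnosis. The form has no second infection row, and no other section reviewed defines infection for objective 2c.

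**Step 2. The plan's own figure.** Section 18.4 wants about 95% certainty of seeing, at least once, a problem with probability 0.05. n = ln(1 − 0.95)/ln(1 − 0.05) = 58.4, rounded up to 59; the approximation is 3/0.05 = 60. The stated 59 reproduces, and this point does not change it.

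**Step 3. How often a case might arise.** The sections reviewed give no deep-infection rate, so p is an assumption. Expected cases in 60 patients = 60p; chance of at least one = 1 − (1 − p)^60.

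| Assumed p | Expected cases | Chance of at least one |
|---|---|---|
| 0.1% | 0.06 | 5.8% |
| 0.5% | 0.3 | 26% |
| 1% | 0.6 | 45% |
| 2% | 1.2 | 70% |

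**Step 4. What one case does to an arm.** With 30 per arm (section 18.4), one case is 1/30 = 3.3 percentage points. Using Clopper-Pearson 95% intervals:

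- Counted: 1/30 = 3.3%, interval 0.1% to 17.2%.
- Not counted: 0/30 = 0%, interval 0% to 11.6% (upper limit 1 − 0.025^(1/30)).

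**Step 5. Agreement between tables.** Suppose an arm has one superficial and one deeper infection. The adverse event count under section 19.1 would be 2/30 (6.7%); the 2c count under the footnote would be 1/30 (3.3%). The protocol gives no rule for reconciling them.

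**The case against.** The strongest defence is that little depends on this item and the case would be seen anyway. Several parts of that stand.

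- **Other routes exist.** A reader might infer that the most serious infections vanish from the study, or that the safety section relies on the form's rate. The documents do not support either reading. Section 19.1 does not refer to the Appendix 8 item; it lists infection as an adverse event without a depth limit, and it requires adverse events to be reported to R&D within 24 hours. With section 16.6, Appendix 13 and the comments line, a deeper infection has several ways onto the record. What remains is that no section says these sources feed the 2c rate.
- **The row has no printed yes/no choice.** Only the stitch-mark item does. An assessor could write in a deep infection. Exclusion is the literal result of the definition, not a certainty in practice.
- **The frequency is unknown.** Wounds are closed with buried subcuticular and percutaneous sutures (section 16.3), and flaps and grafts are excluded (section 18.3). Deep infection may be rare, and the top of the assumed range should not be read as a forecast. A superficial-only outcome would be a defensible choice if the label and objective said so; they do not.
- **The study is descriptive.** Section 17 plans no formal comparison, section 18.4 puts detecting problems ahead of estimating their frequency, and the two intervals in step 4 overlap heavily. This limits the consequence. It does not excuse the definition, since a study meant to see a problem at least once is poorly served by a rule that can leave out a single instance.

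**Conclusion.** The mismatch is real and follows from the protocol's own wording: the form and objective 2c name surgical site infection, and the only definition covers its superficial part. Taken literally, a deeper wound infection is left out of the 2c proportion, and the 2c and adverse event counts could disagree.

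The point is minor. It changes no sample size and no planned comparison, and the case can still be captured elsewhere. Its size rests wholly on the assumed rate: over 0.1% to 2%, the chance that the study meets even one such case runs from about 6% to 70%. If it does, one arm's rate shifts by 3.3 percentage points on an already wide interval. The reason to act is that correction is cheap and the item may be carried into the definitive trial.

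**What to change.** Keep the present Appendix 8 footnote as the definition of a superficial category. Add a second category to the form for infection extending below the subcutaneous tissue, with its own criteria that are not tied to the superficial incision. State that the objective 2c rate is any surgical site infection, reported by arm with its confidence interval, and show the superficial and deep split beneath it.

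Removing the depth clause alone would not be enough. The four criteria would still apply, and a deep infection could fail all of them.

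The cost is a slightly longer form and footnote. Nothing is lost, because the split still gives the superficial-only rate.
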